## **STUDY PROTOCOL**

## Participants

Eligible children with CP who were admitted to Pediatric Rehabilitation outpatient clinic at a tertiary university hospital were enrolled to study according to inclusion criteria. Children with mild-moderate, diplegic or tetraplegic spastic CP aged 3 to 7 years and who had impaired trunk control were recruited to the study. Some of the children were on a wait list for treatments such as botilinium toxin injection, surgery etc. The inclusion criteria were: (1) being classified at Gross Motor Function Classification System (GMFCS) level III-IV; (2) being classified at Manual Ability Classification System (MACS) level III-IV; (3) being able to understand and execute given instructions for evaluations; (4) parental acceptance of using the lycra based compression garment. The exclusion criteria were: (1) serious respiratory restriction (2) having refractory cyanosis or circulatory disorder; (3) having undergone lycra compression orthosis treatment programme previously; (4) having undergone botulinum toxin injection within last 3 months or orthopedic surgery within 1 year; (5) severe scoliosis (Cobb angle (CA) >40°); (6) uncontrolled epilepsy; (7) having intrathecal baclofen pump; (8) having undergone selective dorsal rhizotomy; (9) having reflux more than 3 times a week. The study was conducted after approval from the the institutional Human Research Ethics Committee in accordance with the Declaration of Helsinki. Informed consent was obtained from all legal guardians of the children. Reporting was conducted in accordance with CONSORT14 and recommendations for pilot studies .

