## Study design

The study was designed as prospective, single-blinded, randomized, controlled trial. Children with CP were randomized to either of three groups: SPIO 2 hours, SPIO 6 hours and control group (EKS) which the assessors were blinded to (EG, TO). To ensure group concealment, randomization was done using sealed opaque envelopes which were sequencly numbered in

advance, including the information about which group the child would have been allocated to. The physiotherapist opened the envelopes and started the interventions according to group allocation.

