# Sample size

It was found out that 8 individuals for each group must had been recruited to have 80% power with 5% type 1 error level to detect a minimum clinically significant difference of 1 units of Sitting Assessment Scale score, when the average expected value in the first group was 16.47, with a standard deviation of 1.96 and the average expected value in the second group was 13.20, with a standard deviation of 3.32 based on the previous research conducted by Şimşek et al evaluating the effects of kinesiology taping on trunk control .

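### No stratification of allocation and no adjustment of the analysis for GMFCS level is described, so with 8 children per arm a moderate chance imbalance in severity can go uncorrected

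*Protocol*

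**What the plan says.** **Eligibility.** Protocol, Participants, requires "being classified at Gross Motor Function Classification System (GMFCS) level III-IV". The level is therefore recorded for every child before allocation. The same section also spans MACS III-IV, diplegic and tetraplegic involvement, and ages 3 to 7.

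**Allocation.** Protocol, Study design: "Children with CP were randomized to either of three groups: SPIO 2 hours, SPIO 6 hours and control group". On method it says that "randomization was done using sealed opaque envelopes which were sequencly numbered in" advance. It does not mention how the sequence was generated, or any blocking, stratification or minimisation.

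**Size.** Protocol, Sample size: "8 individuals for each group must had been recruited", which makes 24 children. The aim is "to detect a minimum clinically significant difference of 1 units of Sitting Assessment Scale score".

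**Analysis.** The SAP compares groups by ANOVA, or by Kruskal-Wallis if the data are not normal, with Mann-Whitney tests of pairs at 0.017. Demographic findings are compared by chi-square and t-tests. No covariate is named for any between-group comparison.

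**The concern.** GMFCS level grades gross motor function. The primary outcome, SAS, scores posture and balance in sitting, and a secondary outcome is the sitting dimension of the GMFM. Level III children can reasonably be expected to score higher on both. If one arm happens to receive more of them, its mean rises whatever the garment does.

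Two things could prevent or correct this: stratified allocation and an adjusted analysis. The documents describe neither. Comparing demographic findings between arms could at most reveal an imbalance. At stake are the readability of the three pairwise comparisons and some precision that could be had at almost no cost.

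**Working it through.** **Inputs from the documents.** Three arms of 8. SAS target difference of 1 unit. Expected SAS mean and SD (Protocol, Sample size): 16.47 and 1.96 in one group, 13.20 and 3.32 in the other. Error rates: "to have 80% power with 5% type 1 error level".

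**Assumed inputs.** The documents give neither the mix of levels III and IV nor the SAS gap between them. I take 8, 12 or 16 of the 24 children at level III, and a gap of 2, 3 or 4 SAS units.

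**Step 1. The plan's own figure.**
- Pooled variance = (1.96² + 3.32²)/2 = 7.432, so SD = 2.726. Difference in expected means = 16.47 − 13.20 = 3.27.
- n per arm = 2(z_α + z_β)² × 7.432 / d².
- d = 3.27, one-sided: 2(1.645 + 0.842)² × 7.432 / 10.69 = 8.6, so 9. Two-sided: 10.9, so 11.
- d = 1, two-sided: 2(1.960 + 0.842)² × 7.432 = 116.7, so 117. One-sided: 92.

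Eight per group is thus close to a one-sided test of 3.27 units and far from what 1 unit needs. That is a separate matter, but it limits what any stratification can achieve here.

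**Step 2. How often the levels fall unevenly.** With K children at level III allocated at random to 8/8/8, P(a, b, c) = C(8,a)·C(8,b)·C(8,c) / C(24,K), where a + b + c = K. Summing exactly:

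| K at level III | Given pair differs by ≥3 | At least one of three pairs differs by ≥3 | Given pair differs by ≥4 | At least one pair differs by ≥4 |
|---|---|---|---|---|
| 8 or 16 | 19.3% | 41.8% | 6.5% | 16.2% |
| 12 | 22.0% | 38.6% | 8.4% | 19.1% |

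**Step 3. What that does to SAS.** Shift in an arm difference = (difference in counts / 8) × gap. For 3 children: 3/8 × 2 = 0.75, 3/8 × 3 = 1.125, 3/8 × 4 = 1.5 units.

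The chance that GMFCS imbalance alone moves a given pair by 1 unit or more is:
- gap of 1: 0% in the simulation (it would take all 8 children);
- gap of 2: 7-8% (needs a 4-child difference);
- gap of 3: 19-22% (needs 3);
- gap of 4: 44-46% (needs 2).

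**Step 4. What stratifying and adjusting could gain.** The SE of a pairwise difference is √(7.432 × 2/8) = 1.36. At a 50:50 mix the level contributes variance gap²/4. If all of it were removed:

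| Gap | Remaining variance | SE | Two-sided power for 1 unit |
|---|---|---|---|
| none removed | 7.432 | 1.36 | 11% |
| 2 | 7.432 − 1.00 = 6.432 | 1.27 | 12% |
| 3 | 7.432 − 2.25 = 5.182 | 1.14 | 14% |
| 4 | 7.432 − 4.00 = 3.432 | 0.93 | 19% |

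From all sources together, an SE of 1.36 gives a chance difference of 1 unit or more in 46% of trials with no true effect.

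**The case against.** A reader might infer more than the documents support, in four ways.

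- **That a large imbalance is likely.** It is not. For a given pair, a 3-child difference has a chance of about one in five. The figure for any of the three pairs matters because the SAP tests all three, but it too is below one half.
- **That the imbalance swamps the 1-unit difference.** That depends on a gap between levels that no section gives. At 2 units, a 3-child imbalance stays below 1 unit. A 4-unit gap would take 4.00/7.432 = 54% of the pooled variance, so it is a generous upper end. Against the 3.27-unit difference in expected means, a 1.1-unit shift is about a third.
- **That the comparison is biased.** Chance imbalance under randomisation is not bias. It is already inside the standard error.
- **That allocation is known to be unstratified.** This is inferred from silence. The Protocol neither states nor excludes stratification.

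The choice of factor can also be disputed. SAS includes arm and hand items, so MACS level has a claim. The pre-treatment SAS score, which the Protocol collects, is the more direct covariate. The SAP does not say whether groups are compared on scores or on changes. With changes, much of a gap between levels would cancel. Finally, this is a feasibility and pilot study, and the mismatch in its sample-size statement is the larger problem.

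All of this limits the size of the point. It does not remove it: a severity factor known before allocation is, as far as the documents show, used in neither the allocation nor the analysis.

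**Conclusion.** The point holds as a modest design and analysis weakness. The documents describe no stratification by GMFCS level and plan between-group tests without a GMFCS or baseline term. A difference of 3 or more level III children arises in 19-22% of allocations for a given pair and in 39-42% for at least one pair, if one third to two thirds of the children are at level III. It would move an arm difference by 0.75 to 1.5 SAS units if the levels differ by 2 to 4 units. Both ranges are assumptions.

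The consequence is harder interpretation and lost precision. The precision figures also assume that the pooled SD of 2.726 applies to this population with an even mix of levels. Correcting the weakness would not rescue the 1-unit objective with 8 per arm: power for 1 unit stays at 12-19%.

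**What to change.** **Allocation.** State how the sequence was generated and whether it was stratified. If children are still to be randomised, prepare one sequentially numbered opaque envelope series for GMFCS III and one for GMFCS IV, each in 1:1:1 permuted blocks of randomly mixed size 3 and 6, made up by someone who does not enrol children.

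**Analysis.** Compare SAS and GMFM sitting scores between groups with a linear model that includes arm, GMFCS level and the pre-treatment score. If residuals are clearly non-normal, use a rank-based or permutation version of the same model in place of the unadjusted Kruskal-Wallis and Mann-Whitney tests, which cannot take a GMFCS term. Report GMFCS level by arm.

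If children are already randomised, the adjustment and the table still apply.

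**Cost.** A second set of envelopes, one or two model degrees of freedom, and a change of method for the non-normal case. Incomplete last blocks can leave arm sizes up to 2 apart in each series, so up to 4 in total, which is noticeable among 24 children. No extra visits or patients are needed.

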## Study design

The study was designed as prospective, single-blinded, randomized, controlled trial. Children with CP were randomized to either of three groups: SPIO 2 hours, SPIO 6 hours and control group (EKS) which the assessors were blinded to (EG, TO). To ensure group concealment, randomization was done using sealed opaque envelopes which were sequencly numbered in

advance, including the information about which group the child would have been allocated to. The physiotherapist opened the envelopes and started the interventions according to group allocation.

# Sample size

It was found out that 8 individuals for each group must had been recruited to have 80% power with 5% type 1 error level to detect a minimum clinically significant difference of 1 units of Sitting Assessment Scale score, when the average expected value in the first group was 16.47, with a standard deviation of 1.96 and the average expected value in the second group was 13.20, with a standard deviation of 3.32 based on the previous research conducted by Şimşek et al evaluating the effects of kinesiology taping on trunk control .

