#### **Outcome measures**

The primary outcomes of interest were feasibility and evaluating posture and balance during sitting, therefore SAS was set as the primary outcome measure while secondary outcome measures were Gross Motor Function Measure (GMFM), Box and Block Test (BBT), Parent Satisfaction Survey.

Assessments were conducted before treatment (BT) (TO), at posttreatment (PT), 1 month posttreatment (1 MPT) and 3 months posttreatment (3 MPT) (EG). SAS and BBT were also tested immediately after the orthosis was worn (EG). Children were assessed without the suit on and without any other orthosis except for the assessment of the immediate effect. During the assessment of the immediate effect children wore SPIO under their clothings to hide orthosis from the evaluator.

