3.03.2017

The Effect of Vest Type Dynamic Elastomeric Fabric Orthosis (DEFO) on Sitting Balance and Gross Manual Dexterity in Children With Bilateral Cerebral Palsy: A Feasibility and Randomized, Single-blinded, Pilot Study (NCT03191552)

(Unique Protocol ID:09.2013.0351)

STATISTICAL PLAN

IBM SPSS Statistics for Windows, Version 20,0 (Armonk, NY, USA) will be used to perform all of the analysis. Statistical significance is accepted as $p < 0.05$. Descriptive statistics will be used to determine mean \pm SD of data. Chi-square and t-tests will be used to compare demographic findings. The histogram and normality plots and Shapiro-Wilk normality test were used for data distribution analysis. Between group analysis will be performed using ANOVA if data followed normal distribution. But if not Kruskal-Wallis test will be performed. Mann-Whitney U test was performed to test the significance of pairwise differences using Bonferroni correction (post-hoc test) to adjust for multiple comparisons. For Bonferroni correction, a p value of less than 0.017 ($0.05/3$) was determined as the level of statistical significance

Depending on the distribution analysis, Wilcoxon and dependent t-test will be utilized to detect within group analyzes. To assume changes over time with treatment Friedman and repeated measures analysis of variance will be conducted.

Mann Whitney u and independent sample t-tests will be applied to compare SPIO 2 hours and 6 hours group. To compare groups in pairs in terms of parent satisfaction questionnaire results chi square test will be done.

To evaluate feasibility, recruitment and retention rates will be calculated and percentages will be reported.

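### Eight children per group gives about 10% power (two-sided t-test), not 80%, for a 1-point SAS difference, and the planning means in the same sentence are 3.27 points apart

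*Protocol*

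**What the plan says.** Protocol, Sample size: "8 individuals for each group must had been recruited to have 80% power with 5% type 1 error level", the target being a "minimum clinically significant difference of 1 units of Sitting Assessment Scale score". The same sentence takes its expected values from an earlier study of kinesiology taping. The first group has mean 16.47 and SD 1.96, and for the second "the average expected value in the second group was 13.20, with a standard deviation of 3.32". It does not say which test was assumed, whether it was one- or two-sided, or how the 1-point target and the two means were combined.

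Protocol, Outcome measures: feasibility and sitting posture and balance are the primary interests, and "therefore SAS was set as the primary outcome measure".

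The SAP compares the three groups by ANOVA or Kruskal-Wallis. For the pairwise follow-up, "Mann-Whitney U test was performed to test the significance of pairwise differences using Bonferroni correction (post-hoc test) to adjust for multiple comparisons", and "a p value of less than 0.017 ($0.05/3$) was determined as the level of statistical significance". A separate paragraph adds that "Mann Whitney u and independent sample t-tests will be applied to compare SPIO 2 hours and 6 hours group", with no adjusted level given there.

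**The concern.** One sentence carries two different effect sizes: a 1-point target and planning means more than 3 points apart. A 1-point difference is small against SDs of 1.96 and 3.32, so 80% power from 8 per group is implausible on sight.

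The stake is how the SAS result will be read. The SAP plans significance tests and does not mention confidence intervals. A reader who accepts the power statement could take a non-significant SAS result as evidence against a 1-point benefit. If true power is near 10%, a real 1-point difference would be missed about nine times in ten.

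**Working it through.** **Inputs** (Protocol, Sample size): n = 8 per group, alpha 0.05, power 80%, target 1 point, means 16.47 and 13.20, SDs 1.96 and 3.32. The SAP gives 0.017 for post-hoc pairwise tests. Sidedness and test are not stated, so both sidednesses and several tests were tried.

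**Derived quantities**
- Difference in planning means: 16.47 − 13.20 = 3.27.
- Pooled SD: √((1.96² + 3.32²)/2) = √((3.8416 + 11.0224)/2) = √7.432 = 2.726.
- Standard error of a two-group difference: 2.726 × √(2/8) = 1.363.

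**Trying to reproduce 8 per group with 80% power for 1 point**

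The noncentrality parameter is 1/1.363 = 0.734 on 14 degrees of freedom. The critical value is 2.145 two-sided or 1.761 one-sided.

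| Two-group comparison, 1 point, alpha 0.05 | Power at n = 8 |
|---|---|
| Two-sided t, SD 2.73 | 10.5% |
| One-sided t, SD 2.73 | 17.2% |
| One-sided z, SD 2.73 | 18.1% |
| Two-sided t, smaller SD 1.96 | 15.9% |
| One-sided t, smaller SD 1.96 | 25.0% |
| Three-group ANOVA, extreme groups 1 point apart | 9–10% |

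The stated figure is not reproduced. Reaching 80% for 1 point takes 118 per group (two-sided t) or 93 (one-sided t). With 8 per group it would take an SD of about 0.66 (two-sided) or 0.76 (one-sided); the smaller planning SD is 1.96.

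**Trying 3.27 points instead**

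The noncentrality parameter is 3.27/1.363 = 2.399.

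| 3.27 points, alpha 0.05 | Power at n = 8 |
|---|---|
| Two-sided t, SD 2.73 | 61% |
| Two-sided z, SD 2.73 | 67% |
| One-sided t, SD 2.73 | 74% |
| One-sided z, SD 2.73 | 77% |
| One-sided z, plain mean SD (1.96 + 3.32)/2 = 2.64 | 79.7% |
| Two-sided paired t, SD of differences 2.73 | 83% (75% at n = 7) |

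A two-group t-test with the pooled SD needs 12 per group two-sided or 10 one-sided. The paired t-test returns exactly 8, and the one-sided z-test with SD 2.64 falls just short of 80%. A calculation driven by 3.27 points is therefore a plausible origin of 8, but the documents do not confirm it.

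**At the SAP's pairwise level**
- Two-sided t at 0.017: 4.3% for 1 point, 41% for 3.27 points.
- Mann-Whitney at 0.05/3 for 3.27 points, from 20,000 simulated trials with normal data, the stated SDs and rounding to the integer 5–20 scale: 33% with continuity correction, 35% exact, 36% without correction. Across a common SD and continuous data the range is 31–37%.

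**What 8 per group can deliver** (two-sided t, SD 2.73)
- Difference detectable with 80% power: 4.1 points at 0.05, 4.9 points at 0.05/3. The scale spans 20 − 5 = 15 points.
- Half-width of the 95% interval for a pairwise difference: 2.145 × 1.363 = 2.92 points. Excluding a 1-point benefit would need an observed difference below 1 − 2.92 = −1.92.

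**The case against.** The strongest reply is that 1 point is only a misplaced label and that 3.27 points drove the calculation. That is plausible. Besides the paired t-test, adding a 1-point margin to 3.27 (4.27 points, two-sided t) also returns exactly 8 per group (77% at n = 7, 83% at n = 8). But the protocol describes no margin, and the sentence as written still attaches 80% to 1 point. For the same reason, 118 per group shows the size of the mismatch; it does not show that the trial was planned around 1 point.

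A second reply is that the SAP includes within-group paired tests, and a high within-child correlation could raise power for 1 point. It could: with both SDs set to 1.96 and a correlation of 0.90, a paired t-test has 79% power two-sided and 89% one-sided. The documents give no such correlation, however; the reliability coefficients quoted for the SAS concern raters. With the two stated SDs and a correlation of 0.90, paired power is only 28% or 42%. The sample-size sentence also speaks of a first and a second group, and the trial randomises parallel groups. What stands is that the conclusion should be confined to comparisons between groups on the stated inputs.

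Third, the 0.017 level belongs to post-hoc tests, and the sample-size section makes no claim at that level. That is right: the core error does not depend on it. It matters because the restated power should refer to tests that the SAP will run. The interval depends on the level too: at 0.05/3 the half-width is 2.718 × 1.363 = 3.70 points, so an observed difference of zero would exclude 3.27 points at 95% but not at the adjusted level.

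Last, this is a pilot with feasibility among its primary interests, and nothing in the plan says that a non-significant SAS result will be read as absence of benefit. This softens the consequence and can justify 8 per group. It does not make an explicit power statement correct.

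**Conclusion.** The concern holds and must be fixed. On the protocol's own inputs, a between-group comparison with 8 per group has about 10% power (two-sided t) or 17% (one-sided t) for 1 point, against the stated 80%. For the 3.27 points that separate the planning means, power is 61% to 77% with the pooled SD at 0.05, depending on test and sidedness.

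These figures assume equal groups, a pooled SD of 2.73, approximately normal scores and no baseline adjustment (the SAP plans none). The Mann-Whitney figure also rests on the simulated distribution. The gap for 1 point is far too large for any of the between-group choices tried to close. The origin of 8 remains unknown.

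**What to change.** In Protocol, Sample size, keep 8 per group, delete the claim of 80% power for 1 point, and justify the number on pilot and feasibility grounds. State the difference, test, sidedness and alpha for any power figure that remains. Possible wording:

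> Eight children per group were chosen on feasibility grounds. With an SD of 2.73 and a two-sided t-test, this gives 80% power for a pairwise SAS difference of about 4.1 points at 0.05, or 4.9 points at 0.017. Power for the 3.27-point difference between the planning means is about 61% at 0.05. At 0.017 it is about 41% with a t-test and 34% with the Mann-Whitney test (simulated).

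If one-sided testing was intended, say so and give 74% for 3.27 points at 0.05.

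In the SAP, add one line: SAS group differences are reported with 95% confidence intervals, and non-significance alone is not read as evidence against a 1-point benefit. State also which level applies to the separate comparison of the two SPIO groups, so that the power statement and the tests agree.

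The cost is a reworded paragraph and a short SAP addition. No extra children are needed and conduct does not change. The stated power becomes less favourable.

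### The stated 80% power with 8 children per group is wrong as written: the printed inputs give about 58–61% at two-sided 5%, and the SAP's rule for SPIO v control gives about 36%

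*Protocol*

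**What the plan says.** **Protocol, Sample size.** The section states that "8 individuals for each group must had been recruited to have 80% power with 5% type 1 error level". The target is named as a "minimum clinically significant difference of 1 units of Sitting Assessment Scale score". The inputs are a first-group mean of 16.47 (SD 1.96) and a second-group mean of 13.20 (SD 3.32), taken from an earlier study of kinesiology taping. Neither a third arm nor a corrected significance level is mentioned.

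**Protocol, Study design.** "Children with CP were randomized to either of three groups: SPIO 2 hours, SPIO 6 hours and control group".

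**Protocol, Outcome measures.** SAS is the primary outcome measure; feasibility is also a primary interest.

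**SAP, Statistical Plan.** The general level is given as "Statistical significance is accepted as $p < 0.05". The three arms are compared by ANOVA or Kruskal-Wallis. For pairs, "Mann-Whitney U test was performed to test the significance of pairwise differences using Bonferroni correction (post-hoc test) to adjust for multiple comparisons", and "For Bonferroni correction, a p value of less than 0.017 ($0.05/3$) was determined as the level of statistical significance". A separate sentence compares the two SPIO arms by Mann-Whitney or independent t-test and attaches no 0.017 level.

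**The concern.** The power statement describes one comparison of two groups at 5%. The SAP judges SPIO v control differently: three arms, a rank test and a level one third as large. The 80% therefore does not belong to the analysis that will be run, and any true difference has less chance of being declared than the protocol implies.

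The printed inputs also need checking at the sizing's own 5%. If 8 per group falls short there too, part of the gap has nothing to do with the SAP.

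What is at stake is how a null result is read. Someone who trusts 80% could take a non-significant SPIO v control result as evidence that the garment does nothing, when the design would often miss a difference as large as the one in the taping study.

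**Working it through.** **Inputs (Protocol, Sample size; SAP).** n = 8 per group; means 16.47 and 13.20; SDs 1.96 and 3.32; level 0.05 for the sizing and 0.017 for post-hoc pairs. Neither document states sidedness; two-sided is assumed.

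**Step 1: try to reproduce 8 per group.**
- Difference = 16.47 − 13.20 = 3.27.
- Root-mean-square SD = √((1.96² + 3.32²)/2) = √((3.84 + 11.02)/2) = √7.43 = 2.73.
- Standardised difference = 3.27/2.73 = 1.20.
- Normal approximation: n = 2(z₀.₉₇₅ + z₀.₈₀)²/1.20² = 2(1.960 + 0.842)²/1.44 = 10.9, so 11 per group. The t-test needs 12.
- One-sided 5% needs 9 (normal) or 10 (t-test).
- SD 1.96 in both groups needs 6–7; SD 3.32 in both needs 17–18.
- A true difference of 1 unit needs 117 per group; with 8, power is about 11%.

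None of these gives 8.

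**Step 2: power with 8 per group by t-test.** Noncentrality = 3.27/(2.73 × √(2/8)) = 2.40, with 14 degrees of freedom.

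| Two-sided level | Critical t | Power |
|---|---|---|
| 0.05 | 2.14 | 60.7% |
| 0.017 | 2.71 | 40.9% |

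**Step 3: power under the SAP's rule.** This was simulated with normal scores at the printed means and SDs, unrounded and also rounded and limited to the 5–20 scale. Both SPIO arms are at 16.47 and control at 13.20, with 8 per arm. The Mann-Whitney p-value is the large-sample one without continuity correction.

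| Rule | Power, one SPIO arm v control |
|---|---|
| Mann-Whitney, p < 0.05 | about 58% |
| Mann-Whitney, p < 0.017 | 36–37% |
| Kruskal-Wallis p < 0.05, then Mann-Whitney p < 0.017 | 36–37% |

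- Mann-Whitney at 0.017 with a continuity correction gives 32–34%.
- If the other SPIO arm has half the effect or none, the full rule gives 35–36%.
- At least one SPIO arm is declared different from control in about 47% of trials.
- The three-group Kruskal-Wallis test alone is significant in about 57%.

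**Step 4: split the gap.** On the Mann-Whitney scale, 80 − 58 = 22 points are already missing at 5%, and 58 − 36 = 22 points come from the 0.017 level. On the t-test scale the level costs 61 − 41 = 20 points. About half of the 44-point gap therefore belongs to each fault.

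**Step 5: sensitivity to the SD.** Under the full rule, power per comparison is about 22% if both SDs are 3.32 and about 67% if both are 1.96.

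**Step 6: difference needed for 80% with 8 per group.** A t-test at 0.017 gives 4.91 units, but that is not the SAP's test. Under Kruskal-Wallis then Mann-Whitney at 0.017, power is about 74% at 4.9 units, 76% at 5.0 and 80% at about 5.25.

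**The case against.** **It is a pilot.** The SAP's title calls the trial a feasibility and pilot study, the protocol follows pilot-study recommendations, and recruitment and retention rates are to be reported. This stands, and it lessens the consequence. It does not rescue the statement: the protocol makes an explicit 80% claim and the SAP specifies formal tests.

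**The 36% rests on choices the documents leave open.** Sidedness is not stated, and the three-group test as a first step is inferred from the word post-hoc. The SAP does not say whether raw or change scores are compared, and neither document names SPIO v control as the main contrast. All of this is fair, and the figure should be printed with its assumptions. The first-step test hardly matters (36–37% with or without it). A one-sided 0.017 level would give about 53% by t-test, still short of 80%.

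**Stronger readings that the documents do not support.**
- A reader might infer that the 0.017 level explains the whole fall from 80% to 36%, so that aligning the level would restore 80%. It would not: the printed inputs give only 58–61% at two-sided 5%.
- A reader might infer that every pair of arms is judged only at 0.017. That holds for SPIO v control. The separate SPIO 2 hours v 6 hours sentence carries no such level, and the three-group test runs at the general 0.05.

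**Conclusion.** The power statement is wrong as written. With 8 per group and the printed means and SDs, two-sided power is about 61% (t-test) or 58% (Mann-Whitney) at 5%, and about 36% for each SPIO v control comparison under the SAP's rule. An n that the inputs do not support and a level that the sizing did not use contribute roughly equally.

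The result assumes a true difference of 3.27 units, normal scores before rounding, and all 24 children analysed. The exact figure moves with the SDs (about 22% to 67%), but per-comparison power stays below 80% throughout that range. The named 1-unit target is a further problem in the same sentence: the calculation cannot support it at any of the levels considered.

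The pilot label reduces the practical harm. It does not make the 80% correct.

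**What to change.** In the protocol's Sample size section, replace the 80% claim with the power of the SAP's own rule and state the assumptions. For example:

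> With 8 children per group, assuming two-sided tests, SDs of 1.96 (SPIO) and 3.32 (control) and no dropout, each SPIO v control comparison (Mann-Whitney p < 0.017 after the three-group test) has about 36% power for a 3.27-unit SAS difference (about 22% if both SDs are 3.32, about 67% if both are 1.96). A difference of about 5.25 units would be needed for 80% power.

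Remove the statement that this sample size gives 80% power for a 1-unit difference. Add that a non-significant SPIO v control result in this pilot is not evidence of no effect.

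The cost is a few sentences and a less favourable stated power. No change in enrolment, visits, tests or data is proposed.
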